2.7.3. Investigator Assessment of Bruising Severity Scale

Severity of bruising for each buttock will be documented on the Investigator Assessment of Bruising Severity Scale on Days 1, 2, 4, 7, 14, and 22 (before injection). Investigators will be asked to rate the level of subject bruising using a 5-point photonumeric scale (Table 5):

Rating	Response Option
0	None or almost no bruising
1	Mild Bruising
2	Moderate Bruising
3	Severe Bruising
4	Very Severe Bruising

Table 5:Investigator Bruising Severity Scale

Investigators will document their responses on the corresponding page of the eCRF.

2.7.4. Investigator Bruising Improvement Scale (I-BIS)

On Days 2, 4, 7, 14, and 22 (before injection), the investigator will rate the bruising of the mitigation-treated buttock when compared to the untreated (with mitigation treatment) buttock using the 3-point Likert scale (Table 6). Scores on the higher end of the range indicate greater improvement of bruising with treatment.

Table 6:Investigator Bruising Improvement Scale (I-BIS)

Rating	Response Option
1	Worse (more bruising)
2	Similar
3	Improved (less bruising)

The I-BIS evaluations will be based on live assessments while the subject is in front of the investigator. Note that the I-BIS assessment cannot be completed for subjects that either do not receive mitigation treatment (Cohort 1) or subjects that receive bilateral mitigation treatment (as in Cohort 2), as there is no untreated buttock for comparison.

2.7.5. Investigator-Global Aesthetic Improvement Scale (I-GAIS)

On Days 22, 43, and 71, the investigator will determine the degree of improvement of each of the buttocks by comparing the cellulite by live assessment on Days 22, 43, and 71 to the Day 1 pre-treatment (Baseline) image of that buttock (Table 7). The investigator will provide a separate rating for each buttock from the I-GAIS and enter the results on the corresponding page of the eCRF.

Rating	Response Option	Description
+3	Very much improved	Optimal cosmetic result from treatment of the treated dimples
+2	Much improved	Marked improvement in the treated area appearance from before treatment, but not completely optimal
+1	Improved	Obvious improvement in the treated area appearance from before treatment, but additional treatment is indicated
0	No change	The treated area appearance is essentially the same as before treatment
-1	Worse	The treated area appearance is worse than before treatment
-2	Much worse	Marked worsening in appearance from the initial condition
-3	Very much worse	Obvious worsening in appearance from the initial condition

 Table 7:
 Investigator Global Aesthetic Improvement Scale (I-GAIS)

2.8. Subject Assessment Ratings

2.8.2. Subject Bruising Improvement Scale (S-BIS)

On Days 2, 4, 7, 14, and 22 (before injection), the subject will rate the bruising of the mitigationtreated buttock when compared to the untreated (with mitigation treatment) buttock using the 3-point Likert scale (Table 8). Scores on the higher end of the range indicate greater improvement of bruising with treatment.

Table 8:Subject Bruising Improvement Scale (S-BIS)

Rating	Response Option	
1	Worse (more bruising)	
2	Similar	
3	Improved (less bruising)	

Note that the S-BIS assessment cannot be completed for subjects that either do not receive mitigation treatment (Cohort 1) or subjects that receive bilateral mitigation treatment (as in Cohort 2), as there is no untreated buttock for comparison.

2.8.3. Patient Bother by Bruising Scale

On Days 4, 7, and 22 (before injection), subjects will indicate their level of bother by bruising for each buttock using a 4-point scale. Subjects were asked "Thinking about the bruising on your

left/right buttock, how bothered are you with the appearance of the bruising on your left/right buttock?" and asked to respond using one of the following ratings (Table 9):

Rating	Description
1	Not at all bothered
2	A little bothered
3	Moderately bothered
4	Extremely bothered

Table 9:Patient Bother by Bruising Scale

Subjects may use a mirror, or photographs captured by the subject or another person with the subject's imaging device (ie cell phone, digital cameras) or images captured by the investigator or designee using the site's digital photography system.

2.9. Skin Assessment (Fitzpatrick Scale)

At the Screening Visit, subject skin type will be evaluated by the Investigator using the Fitzpatrick Scale (Table 10). Only subjects with a Fitzpatrick skin rating of I-III at the Screening Visit will be included in the study.

Table 10:Fitzpatrick Scale

Rating	Response Option	Description
Ι	Pale white skin, blue/hazel eyes, blond/red hair	Always burns, does not tan
II	Fair skin, blue eyes	Burns easily, tans poorly
III	Darker white skin	Tans after initial burn
IV	Light brown skin	Burns minimally, tans easily
V	Brown skin	Rarely burns, tans darkly easily
VI	Dark brown or black skin	Never burns, always tans darkly

2.10. Weight, Height, and BMI

At the Screening Visit, height and weight measurements will be taken. Baseline body mass index (BMI) will be computed from these measurements as the weight in kilograms (kg) divided by height in meters squared (m²).

Body weight will also be measured at the Day 71/ET visit; BMI will be computed from this measurement using the height at Screening.

2.11. Adverse Events

Adverse Events (AEs), including both observed or volunteered problems, complaints, signs or symptoms must be recorded, regardless of whether associated with the use of study treatment. Study treatment includes QWO (CCH-aaes) and mitigation treatments.

The following information will be collected for all AEs:

- Verbatim description
- Injection Site Reaction (Yes/No)
- Date of Onset

- Date of Resolution/or Ongoing
- Severity (Mild, Moderate, Severe)
- Relationship to QWO (CCH-aaes) (Not Related, Unlikely Related, Possibly Related, Probably Related)
- Action taken with QWO (CCH-aaes) (None, Interrupted, Withdrawn)
- Relationship to Mitigation Treatment (Not Related, Unlikely Related, Possibly Related, Probably Related)
- Action taken with Mitigation Treatment (None, Interrupted, Withdrawn)
- Outcome (Recovered/Resolved, Recovered/Resolved w/Sequelae, Recovering/ Resolving, Not Recovered/Not Resolved, Fatal, Unknown)
- Whether or not a concomitant medication or procedure was required
- Classified as a serious adverse event (SAE) or not
- SAE Code (Death, Life-threatening, Inpatient or prolonged hospitalization, Persistent or significant disability/incapacity, Congenital anomaly or birth defect, Other medically important event)

2.12. Medical History

Medical history and cellulite history, including all prior procedures to treat cellulite, will be obtained at the Screening Visit. Medical history will include a review of the following systems: general, dermatological, respiratory, cardiovascular, gastrointestinal, genitourinary, gynecological, endocrine, musculoskeletal, hematological, neuropsychological, immune (allergies), and head, eyes, ears, nose, and throat. Historical and current medical conditions including date of last menstrual period will be recorded.

History of tobacco and alcohol use (never, current, former) will also be collected.

Surgical history will include a review of all surgical procedures completed in the prior 5 years and any surgery completed at any time in the treatment area.

2.13. Physical Examination

A limited physical examination will include evaluation of height, weight, lungs, heart, abdomen, and extremities will be conducted at the Screening Visit. Weight will also be recorded at the Day 71/ET visit.

2.14. Vital Signs

Temperature, pulse, systolic blood pressure, and diastolic blood pressures will be collected at the Screening Visit, and before the first QWO (CCH-aaes) injection and approximately 30 minutes after injection on Day 1. Pulse and blood pressure will be collected after the subject has been sitting for 5 minutes. The investigator will review all vital sign values for clinical significance. Any vital sign value meeting the investigator's criteria for clinical significance will be recorded as an AE (or SAE, if appropriate).

2.15. Pregnancy

All pregnancies in subjects identified during or after this study, where the estimated date of conception is determined to have occurred during the study or within 28 days of the last study treatment in subjects who terminate the study early, must be reported, followed to conclusion, and the outcome reported, even if the subject is discontinued from the study.

Subjects will be instructed to immediately notify the investigator of any pregnancies.

Pregnancy itself is not regarded as an AE unless there is suspicion that the investigational product under study may have interfered with the effectiveness of a contraceptive medication. Likewise, elective abortions without complications are not considered AEs. Any SAEs associated with pregnancy, including spontaneous miscarriages, must additionally be reported and handled as SAEs.

A subject who becomes pregnant must be withdrawn from the study.

2.16. Prior and Concomitant Medications and Procedures

Any prior medications and nondrug therapies (eg, blood transfusions, oxygen supplementation, physical therapy, etc.), including all prior medications and/or procedures for cellulite, taken within the 30 days prior to the Baseline Visit will be recorded. Any concomitant medications and/or nondrug therapies received from the Baseline Visit through the Day 71 Visit will also be recorded. Mitigation treatments administered after each treatment session of QWO (CCH-aaes) may be recorded as concomitant medications or procedures, as appropriate.

2.16.1. Prohibited Medications

During the study, the following treatments are prohibited:

- Anticoagulants (ie, warfarin [Coumadin] heparin analogues)
- Antiplatelet medications (eg, clopidogrel [Plavix], aspirin)

2.16.2. Suggested Concomitant Medications and Procedures

During the study, acetaminophen will be permitted to treat pain at the injection site as needed. Other required concomitant medications may be administered at the investigator's discretion.

2.17. COVID-19 Related Protocol Deviations

All study assessments conducted outside of the allowed windows outlined in the schedule of assessments due to a COVID-19 interruption will be documented as a protocol deviation. COVID-19 will be recorded as the reason for these out-of-window assessments.

3. STUDY PARAMETERS

3.1. Subject Disposition

Subjects will be considered as completing the study if they complete the Day 71 visit. Subjects who do not complete the study will report their reason for early discontinuation.

Time in the study (days) will be computed as the date of last visit minus the date of Day 1 + 1, where the date of the last visit is determined as the following:

- The date of Day 71 if the subject completes the study
- The date of early termination visit if the subject is terminated early from study at a non-scheduled visit
- The date of the latest scheduled visit if the subject is terminated early from study at a scheduled visit or lost to follow-up

3.2. Early Termination Visit Assessments

Subjects who discontinue study treatment (QWO [CCH-aaes] or mitigation treatment) or are withdrawn from the study will be encouraged to complete the remaining study visits and evaluations, including providing any additional follow-up information, unless the subject specifically indicates that they will not participate in any further evaluations.

Subjects who discontinue or are withdrawn from the study at any time after the first dose of the study treatment (QWO [CCH-aaes] and mitigation treatments) will not be replaced.

Permanent study discontinuation is required if the subject becomes pregnant during the study.

3.3. Study Treatment

Subjects will be divided into 1 of 6 treatment cohorts (different mitigation treatments along with the same QWO treatment). Subjects will first receive up to 0.84 mg of QWO (CCH-aaes) injected subcutaneously per buttock with both buttocks treated. There will be 3 treatment visits at intervals of 21 days as described in the schedule of assessments. Mitigation treatments will be provided locally by each investigator/subject, and can be administered after each treatment session of QWO (CCH-aaes).

3.3.1. QWO (CCH-aaes) Assessments

To induce a similar extent and severity of bruising in each buttock, approximately the same number of injections (up to 12 per buttock) will be administered to the left and right buttock; however, the number of injections per buttock may differ among treatments as dimples improve.

The number of injections administered at each treatment session will be recorded for each buttock. The difference in the number of injections administered will be computed for each subject for each QWO treatment session as (number of QWO injections in left buttock) – (number of QWO injections in right buttock). A positive difference is indicative of more injections in the left buttock, while a negative difference is indicative of more injections in the right buttock.

3.3.2. Mitigation Assessments

Mitigation treatments administered after each treatment session of QWO (CCH-aaes) will be recorded on the Study Mitigation Treatment page of the eCRF. The start and stop date, type of mitigation treatment, and location (left and/or right buttock) will be recorded and assessed.

Mitigation treatments may also be recorded as concomitant medications or procedures; these treatment records will be included in corresponding assessments (see section 3.6.2).

3.3.3. Cohorts

The cohorts will be structured as described in Table 1, and will be summarized by the mitigation treatment used:

- Cohort 1: No mitigation treatment (control)
- Cohort 2: Compression garments
- Cohort 3: Instant cold packs
- Cohort 4: Arnica gel patches (OcuMend)
- Cohort 5: INhance post-injection serum with TriHex technology
- Cohort 6: Pulse Dye Laser (PDL) treatment

Once subjects are assigned to a particular cohort using the site-specific Mitigation Treatment Assignment Table, the cohort assignments will remain regardless of the actual treatment received. Subjects who receive a different mitigation treatment at any time from the mitigation treatment to which they were assigned will be reported as a protocol deviation.

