9.3.2. Safety Analyses

All subjects who receive at least 1 dose of QWO [CCH-aaes] with or without mitigation treatment will be included in the safety analyses. Subjects will be included in the safety analyses based on the actual mitigation received.

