4. ANALYSIS POPULATIONS

4.1. Safety Population

The Safety Population is defined as all subjects allocated to treatment who receive at least 1 injection of QWO (CCH-aaes) with or without mitigation treatment. All demographic and baseline characteristics, as well as safety parameters, will be summarized based on this population.

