5. STATISTICAL METHODS

5.1. Overview

The primary efficacy endpoint will be summarized as frequency counts and percentages based on the Evaluable Population by cohort. Mean and standard deviation (SD) will also be provided.

The secondary and supportive efficacy endpoints except for change from baseline measures will be summarized as frequency counts and percentages based on the Evaluable Population by cohort and by buttock, where appropriate. The change from baseline measures will be summarized using descriptive statistics (n, mean, SD, median, minimum and maximum).

TEAEs will be summarized as frequency counts and percentages by preferred term and by cohort. The results and change from baseline for vital signs will be summarized using descriptive statistics.

Subject listings of all data from the eCRFs as well as any derived variables will be presented.

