5.7.5. Exploratory Endpoints –

5.8. Safety Evaluation

5.8.1. Adverse Events

The following listings will be provided based on all AEs:

- Listing of deaths.
- Listing of non-fatal SAEs.
- Listing of non-serious AEs leading to discontinuation from study.

Listing of non-serious AEs leading to interruption or discontinuation of either QWO (CCH-aaes) or mitigation treatment. The following summary tables of AEs will be presented by cohort:

- TEAEs
 - Overall summary
 - By preferred term
 - By preferred term and severity
 - By frequency of SAEs
 - By frequency of most common non-SAE
- QWO-related AEs
 - Overall summary
 - By preferred term
 - By preferred term and severity
- Mitigation-related AEs
 - Overall summary
 - By preferred term
 - By preferred term and severity

The overall summary will consist of the following items:

- Total number of AEs
 - All AEs
 - Mild AEs
 - Moderate AEs
 - Severe AEs
 - Related to QWO (CCH-aaes) Only (TEAEs overall summary only)
 - Related to Mitigation Only (TEAEs overall summary only)
 - Related to both QWO (CCH-aaes) and Mitigation (TEAEs overall summary only)
- Total number of subjects with
 - At least 1 AE

- At least 1 SAE
- At least 1 severe AE
- No severe AEs but at least 1 moderate AE
- No severe/moderate AEs but at least 1 mild AE
- At least 1 AE leading to discontinuation from study
- At least 1 AE leading to interruption or discontinuation of QWO (CCH-aaes) only (TEAE overall summary only)
- At least 1 AE leading to interruption or discontinuation of Mitigation Treatment only (TEAE overall summary only)
- At least 1 AE leading to interruption or discontinuation of both QWO (CCH-aaes) and Mitigation Treatment (TEAE overall summary only)
- Total number of subjects who died (TEAEs overall summary only)

Percentages for the total number of mild, moderate, and severe AEs will be based on the total number of all AEs in the cohort.

The by frequency summaries will also include the total number of occurrences the AE preferred term was reported as well the number of subjects with at least 1 report of the AE. Most common non-SAEs are any preferred term AE that at least 5% of the subjects in any cohort report at least once.

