5.8.2. Weight and BMI

Weight and BMI at baseline, Day 71/ET, and change from baseline will be summarized by treatment cohort.

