5.8.3. Vital Signs

Vital signs on injection day will be summarized at baseline (pre-injection) and post-injection time points (30 minutes after injection) and change from baseline by treatment cohort. The baseline value will be based on the pre-injection measurement at each treatment session. A listing of all vital sign information will be provided.

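### The SAP's cohort rule places subjects in the safety tables by assigned mitigation, whereas Protocol 9.3.2 groups them by the mitigation received

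*SAP*

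**What the plan says.** Protocol 9.3.2 sets the grouping rule for safety: "Subjects will be included in the safety analyses based on the actual mitigation received". Protocol 9.3.2.1 then calls for adverse event summaries for each mitigation group.

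SAP 3.3.3 is the only place where the SAP defines cohort membership. It introduces the list of six cohorts by saying that they "will be summarized by the mitigation treatment used". After the list it states the rule: once a subject is assigned, "the cohort assignments will remain regardless of the actual treatment received". Receipt of a different mitigation is to be reported as a protocol deviation. Regrouping is not mentioned.

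The safety sections of the SAP use cohort throughout:

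- SAP 5.1: "TEAEs will be summarized as frequency counts and percentages by preferred term and by cohort".
- SAP 5.8.1: "The following summary tables of AEs will be presented by cohort".
- SAP 5.8.2: "Weight and BMI at baseline, Day 71/ET, and change from baseline will be summarized by treatment cohort".
- SAP 5.8.3: results at each time point "and change from baseline by treatment cohort".

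The safety shells carry columns for Cohorts 1 to 6. SAP 4.1 defines who is in the Safety Population and adds "All demographic and baseline characteristics, as well as safety parameters, will be summarized based on this population", with no as-received rule. SAP Table 11 derives no variable for actual mitigation. SAP section 10 reserves Table 14 for significant changes from the protocol; in the public text it has column headings, no entries and no redaction mark.

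**The concern.** The two rules cannot both be followed for a subject whose assigned and received mitigation differ. A programmer working from the SAP would leave her in the assigned column.

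The safety objective concerns CCH-aaes combined with mitigation, and the SAP plans separate tables of mitigation-related events. Under the SAP rule, an event attributed to one mitigation could be counted as mitigation-related under another, or under the No Mitigation column.

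Both documents foresee such a mismatch: the protocol has an as-received rule and the SAP a deviation rule. Features of the design make it possible. Cohort is assigned at Screening (Protocol 6.3.1). Mitigations are sourced locally and several are used at home (Protocol 6.2.2). Exclusion criterion 16 can rule out laser treatment for a subject already allocated to it (Protocol 5.2). The opportunity is limited, however: later sessions allow only the same mitigation as the first (Protocol 4.2), so a mismatch needs either a deviation or failure to receive the assigned mitigation.

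**Working it through.** **Step 1: the texts side by side.**

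| Question | Protocol | SAP |
|---|---|---|
| Grouping for safety | Mitigation received (9.3.2) | By cohort (5.1, 5.8.1 to 5.8.3) |
| Meaning of cohort | Not defined as overriding 9.3.2 | Fixed by assignment (3.3.3) |
| Safety exception | Not needed | None (3.3.3, 4.1) |
| Variable for actual mitigation | n/a | None (Table 11) |
| Change declared | n/a | No entry (Table 14) |

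The SAP safety sections do not themselves say as assigned. That follows from applying the only definition of cohort in the SAP.

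**Step 2: the plan's own figure.** Protocol 9.1 and SAP 8 give 6 cohorts of about 8: 6 × 8 = 48, as stated. No alpha, power or effect size is given, and none is needed here.

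**Step 3: effect of one misplaced subject.** Assume exactly 8 per cohort and one subject who moves from the assigned column to the received column. Let a and b be the numbers with the event, out of 8, in the column left and the column joined under the SAP rule. Let x = 1 if the moved subject has the event and 0 if not.

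- Column left: (a − x)/7 − a/8 = (a − 8x)/56.
- Column joined: (b + x)/9 − b/8 = (8x − b)/72.

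The largest absolute values are 7/56 = 12.5 points (a = 1, x = 1, or a = 7, x = 0) and 8/72 = 11.1 points (b = 0, x = 1, or b = 8, x = 0).

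| Case (moved subject has the event) | Column left | Shift | Column joined | Shift |
|---|---|---|---|---|
| Rare: a = 1, b = 0 | 1/8 = 12.5% to 0/7 = 0% | 12.5 | 0/8 = 0% to 1/9 = 11.1% | 11.1 |
| Middle: a = b = 4 | 4/8 = 50.0% to 3/7 = 42.9% | 7.1 | 4/8 = 50.0% to 5/9 = 55.6% | 5.6 |
| Common: a = b = 7 | 7/8 = 87.5% to 6/7 = 85.7% | 1.8 | 7/8 = 87.5% to 8/9 = 88.9% | 1.4 |

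With 1, 2 or 3 subjects moving the same way, the denominators become 7 and 9, 6 and 10, or 5 and 11. The documents give no crossover rate, so these numbers of movers are assumptions.

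**The case against.** The strongest reply has three parts.

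First, SAP 3.3.3 opens with "will be summarized by the mitigation treatment used", which could be taken as an as-received rule. In its place it introduces the cohort labels, and the explicit sentence after the list governs membership. If the two are read as conflicting, the SAP contradicts itself and still needs amending.

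Second, a SAP may refine a protocol. It may, but Table 14 exists to record such changes, and no entry appears there or elsewhere in the SAP.

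Third, nothing is lost. A reader might infer that crossovers would be hidden, and the documents do not support that. SAP 3.3.3 makes receipt of a different mitigation a deviation, and Listing 16.2.2 shows deviations by subject. Table 14.2.2 shows the type received within Cohorts 2 to 6. Listing 16.2.5.2 gives mitigation type, dates and location and is headed for all enrolled subjects, so use in Cohort 1 can appear there. Relationship to mitigation is recorded for each event, separately from relationship to CCH-aaes. This stands and lowers the weight of the point. It does not move the subject's events out of the wrong column: deviations are listed and not summarized (SAP 5.4), and Table 14.2.2 leaves out Cohort 1.

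A reader might also infer that vital-sign comparisons would be seriously distorted. The documents do not support that either. Vital signs are analyzed on Day 1 only, before the dose and about 30 minutes after injection (SAP 2.14, 3.5.2), and the laser may be given as late as Day 7. Moving a subject there would mostly move baseline differences between people. The adverse event tables are where the grouping matters.

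**Conclusion.** The inconsistency is established: applied as written, the SAP rule gives safety tables that depart from Protocol 9.3.2 for any subject whose received mitigation differs from her assignment. It should be corrected before database lock.

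Its effect is contingent. It is nil if all subjects receive their assigned mitigation and no other. Otherwise one whole-subject move shifts an event rate by at most 12.5 and 11.1 points in the two columns, and by 1.8 and 1.4 points for an event at 7/8 in both that the moved subject has. These figures assume 8 per cohort and a single mover. The safety analysis is descriptive and the SAP plans no formal comparison of efficacy between mitigations, so no test or error rate is affected.

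It would go too far to say that misattribution will occur, since no crossover rate is given, or that assigned cohort is wrong for efficacy, since the protocol's as-received rule is stated for safety. The statement that no change is declared rests on Table 14 as it appears in the public text.

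**What to change.** 1. Add to SAP Table 11 a subject-level variable for actual mitigation, derived from the Study Mitigation Treatment page of the eCRF. SAP 3.3.2 already has type, dates and location recorded there.
2. Use it as the column variable for the safety tables, above all the adverse event tables. Keep assigned cohort for efficacy. Amend SAP 3.3.3, 5.1 and 5.8 to say so.
3. Have the sponsor pre-specify how a subject is classed if she receives more than one type, or receives mitigation only at a later session. The documents do not dictate that choice. A class based on the first session alone would put a subject mitigated only later under No Mitigation, so the rule needs thought. Footnote and list such subjects.
4. If assigned cohort is preferred for safety, enter that departure from Protocol 9.3.2 in Table 14 with a justification.

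Cost: a few sentences, one derived variable and relabelled safety columns, with no new data. The downside is that column denominators in the safety tables may differ from those in the efficacy tables and from the other Safety Population tables kept by assigned cohort (demographics, exposure, concomitant therapy). A footnote should explain this.
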